13.1.2 Primary Efficacy Endpoint for Phase II

The primary endpoint is time to clinical improvement as measured by OSCI. Time to clinical improvement by OSCI is defined as the time from the date of randomization to the first date of clinical improvement measured by OSCI. Subjects who do not have clinical improvement on or before Study Day 28 will be censored at Study Day 28.

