6.9. Efficacy Endpoint Definitions

- **Time to Clinical Improvement by OSCI**: defined as the time from the date of randomization to the first date of clinical improvement measured by OSCI. (Appendix D). Clinical improvement is defined as an improvement at least by cross category (or Patient State improvement in Appendix D table, such as from Hospitalized Severe Disease to Hospitalized Mild Disease). Subjects who do not have clinical improvement on or before Study Day 28 will be censored at Study Day 28.
- **Clinical Status by OSCI**: defined by the Ordinal Scale score of 0 to 8 by OSCI (Appendix D).
- **Rate of Clinical Improvement by OSCI**: defined as the proportion of subjects who achieved clinical improvement by OSCI.
- **Time to Clearance of SARS-CoV-2**: defined as the time from the date of randomization to the clearance of SARS-CoV-2 by rRT-PCR by two negative results at least 24 hours apart, with the first negative as the start date of clearance. Specimens included are nasopharyngeal swab and oropharyngeal swab (if available). Subjects who do not have clearance on or before Day 28 will be censored at Day 28.
- **Rate of Clearance of SARS-CoV-2**: defined as the proportion of subjects with “negative” measurement of COVID-19 by rRT-PCR.
- **Time to Clinical Improvement by NEWS2**: defined as the time from the date of randomization to the first date of clinical improvement. Clinical improvement is defined as improvement of clinical symptoms as measured by the NEWS2 Score (Appendix C). Subjects who do not have clinical improvement on or before Study Day 28 will be censored at Study Day 28.
- **Rate of Clinical Improvement by NEWS2**: defined as the proportion of subjects who achieved clinical improvement.
- **Time to Pulmonary Clearance**: defined as the time of randomization to the date of pulmonary clearance. This is defined as disappearance of virus from LRT- specimen where it has previously been found (induced sputum if available, endotracheal aspirate if available). Subjects who do not have pulmonary clearance on or before Study Day 28 will be censored at Study Day 28.
- **Pulmonary Clearance Rate**: defined as the proportion of subjects who achieve pulmonary clearance.

- **Duration of Hospitalization:** defined as date of randomization to the date of medical discharge. Subjects who are not discharged on or before Study Day 28 will be censored at Study Day 28.

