8. SELECTION AND WITHDRAWAL OF SUBJECTS

8.1. Subject Inclusion Criteria

1. Subject has confirmed positivity for SARS-CoV-2 as measured by rRT-PCR or other approved test to detect SARS-CoV-2 per institutional practice.
2. Subject is experiencing any symptom/clinical sign of COVID-19 illness or has a positive disease-related chest x-ray/CT scan at screening.
3. Subject is ≥ 18 years of age at the time of signing the Study informed consent form (ICF).
4. Subject understands and voluntarily signs the Study ICF prior to any study-related assessments/procedures are conducted.
5. Subject is willing and able to adhere to the study schedule and other protocol requirements.
6. $\text{SpO}_2 \geq 88\%$ on room air; oxygen is permitted as delivered by nasal cannula and/or face mask at any flow rate to achieve this SpO_2 . Subjects must have an $\text{SpO}_2 \geq 92\%$ if on supplementary oxygen.
 - *(Note: Once eligibility is confirmed, to initiate CYNK-001 treatment, an increase of supplemental oxygen of greater than or equal to 50% from baseline/screening resulting in oxygen use of greater than 8L -or- a change in mode of supplemental oxygen delivery with the intention to deliver oxygen more frequently requires consultation with the medical monitor)*
7. Ability to be off immunosuppressive drugs for 3 days prior to infusion, unless clinically indicated. Steroids are permitted if clinically indicated and at the discretion of the treating physician. If clinically indicated, careful consideration should be taken regarding the timing and tapering of high-dose steroids.
8. Female of childbearing potential (FCBP)* must not be pregnant and agree to not becoming pregnant for at least 28 days following the last infusion of CYNK-001. FCBP must agree to use an adequate method of contraception during the treatment period.
 - a. *FCBP is a female who: 1) has achieved menarche at some point, 2) has not undergone a hysterectomy or bilateral oophorectomy or 3) has not been naturally postmenopausal (amenorrhea following cancer therapy does not rule out childbearing potential) for at least 24 consecutive months (i.e., has had menses at any time in the preceding 24 consecutive months).
9. Male subjects must agree to use a condom during sexual contact for at least 28 days following the last infusion of CYNK-001, even if he has undergone a successful vasectomy.

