14.6. Efficacy Analysis

Phase I efficacy data will be summarized by descriptive analyses. The efficacy endpoints used in the lack of efficacy tests is the responses at Day 15 of the clinical improvement by OSCI. If efficacy is not established in 2 out of the 14 subjects, the study will be terminated. If efficacy is noted in 2 or more subjects, the study will move forward to the Phase II portion.

Efficacy endpoints are defined in [Section 6.9](#).

Phase II efficacy data will be summarized by descriptive analyses. The efficacy endpoints used in the lack of efficacy tests is the responses at Day 15 of the clinical improvement by OSCI. If efficacy is not established in 2 out of the 14 subjects, the study will be terminated. If efficacy is noted in 2 or more subjects, the study will move forward to the Phase III portion.

No interim analysis will be implemented in this study.

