APPENDIX D. ORDINAL SCALE FOR CLINICAL IMPROVEMENT

Patient State	Descriptor	Score
Uninfected	No clinical or virological evidence of infection	0
Ambulatory	No limitation of activities	1
	Limitation of activities	2
Hospitalized Mild disease	Hospitalized, no oxygen therapy	3
	Oxygen by mask or nasal prongs	4
Hospitalized Severe Disease	Non-invasive ventilation or high-flow oxygen	5
	Intubation and mechanical ventilation	6
	Ventilation + additional organ support – pressors, RRT, ECMO	7
Dead	Death	8

Source: [World Health Organization \(WHO\) R&D Blueprint novel Coronavirus; COVID-19 Therapeutic Trial Synopsis, 2020.](#)

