13.1 Primary Efficacy Endpoint

13.1.1 Primary Efficacy Endpoint for Phase I

The efficacy analysis for Phase I will be based on the safety analysis population.

The primary efficacy endpoint for Phase I is clinical improvement by OSCI on or prior to Day 15. Clinical improvement by OSCI is defined as at least one patient state improvement compared to baseline. If clinical improvement by OSCI is demonstrated for at least 2 out of 14 subjects on or prior to Study Day 15, and CYNK-001 is deemed to be safe, the study will move to Phase II. Otherwise, the study will be terminated.

Phase I efficacy data will be summarized by descriptive analyses for the number and proportion of subjects who achieved clinical improvement by OSCI by Day 15.

The proportion of the clinical improvement by OSCI at Day 15 will be summarized with a point estimate, standard error and a 95% confidence interval.

Patients who do not achieve at least one patient state improvement will be considered as failure to improve by OSCI. No formal hypothesis testing will be carried out for this part of the analysis.

Subject listings of clinical status using OSCI will be provided.

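### The first day in a better OSCI Patient State is a permanent success: a subject who improves, relapses and dies by Day 28 counts as improved, while a subject who dies without improving counts as never improved

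*SAP*

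**What the plan says.** **Timing and size of the event.** SAP 13.1.2 measures "the time from the date of randomization to the first date of clinical improvement measured by OSCI", and Protocol 6.9 has the same timing. On the size of the change, Protocol 6.9 states: "Clinical improvement is defined as an improvement at least by cross category". SAP 13.1.1, in its Phase I text, states: "Clinical improvement by OSCI is defined as at least one patient state improvement compared to baseline". The SAP's Phase II paragraph does not repeat a size rule, so it is taken from these two places. Protocol 11 has OSCI recorded every day, by phone once the subject is an outpatient. SAP 4.7 uses the last observation of the study day.

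**The scale and entry.** In Protocol Appendix D the severe hospitalized state starts at score 5, "Non-invasive ventilation or high-flow oxygen". The mild hospitalized state ends at score 4, "Oxygen by mask or nasal prongs". Inclusion criterion 6 (Protocol 8.1) says "oxygen is permitted as delivered by nasal cannula and/or face mask at any flow rate".

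**Death and sensitivity.** SAP 13.3 censors at Day 28 a subject who dies without having improved. It does not mention death after an improvement. The only sensitivity analysis (SAP 13.4) repeats the endpoint, with the same definition, in the per-protocol population.

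**Phase I gate.** SAP 13.1.1 sets the condition "If clinical improvement by OSCI is demonstrated for at least 2 out of 14 subjects on or prior to Study Day 15". Protocol 14.6 says the measure used "is the responses at Day 15 of the clinical improvement by OSCI", and the Synopsis also refers to Day 15 responses.

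**The concern.** One end-of-day score in a better Patient State settles the subject's outcome. Neither document asks for a confirming score, a minimum duration, survival, or freedom from readmission.

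Censoring deaths at Day 28 has a clear purpose: it keeps a subject who dies in the risk set as someone who never improved. As worded, though, the rule depends on the order of events. The same death is a failure if no improvement came first and is ignored if one did.

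Three things are at stake. A death can sit among the successes of the primary analysis. Improvements that do not last add events unrelated to treatment and pull the rate ratio toward 1 when they are equally common in both arms. In Phase I, where two responders of 14 open the gate, a subject who improved briefly can be one of the two under one wording and not under the other.

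**Working it through.** **Step 1. Apply the rules to example records.** Randomization on Day 1 is assumed. The last two columns use the changes set out under the fix.

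| Record | As written | Primary with death rule extended | Sustained analysis |
|---|---|---|---|
| Baseline 4, discharged Day 8 (score 2), readmitted Day 10 (score 5), dies Day 20 | Event Day 8 | Censored Day 28 | Censored Day 28 |
| Baseline 4, never discharged, dies Day 20 | Censored Day 28 | Censored Day 28 | Censored Day 28 |
| Baseline 4, discharged Day 8, readmitted Day 10, alive in hospital Day 28 | Event Day 8 | Event Day 8 | No event |
| Baseline 5, scored 4 on one day, 5 again from the next day to Day 28 | Event on that day | Event on that day | No event |
| Baseline 4, worsens to 5, returns to 4, still in hospital Day 28 | No event | No event | No event |
| Baseline 4, moves to 3, still in hospital Day 28 | No event | No event | No event |

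The first two rows show the inconsistency. The last three show the limit of the device route: improvement is relative to baseline and must cross a Patient State, so a one-day device change is an event only for a score-5 baseline. For a baseline of 3 or 4 the event is discharge.

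**Step 2. Reproduce the planned power.** Inputs from the Protocol Synopsis and SAP 6: 36 per arm, times of 8 and 16 days (read as exponential medians), 28 days of follow-up, one-sided 0.05, power of at least 81%.

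- P(event by Day 28) = 1 − 2^(−28/median): 1 − 2^(−3.5) = 0.912 and 1 − 2^(−1.75) = 0.703.
- Expected events = 36 × (0.912 + 0.703) = 58.1.
- Freedman: √58.1 × (1 − 0.5)/(1 + 0.5) − 1.645 = 0.896, power 81.5%. Schoenfeld gives 84.1% and a simulated log-rank test 84%.

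The stated figure is reproduced. It makes no allowance for transient improvement.

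**Step 3. Illustrate dilution (assumed rates).** Let sustained improvement have medians 8 and 16 days, and add a transient hazard with median m, equal in both arms. The observed rate ratio is (1/8 + 1/m)/(1/16 + 1/m).

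| m (days) | Rate ratio | Expected events | One-sided power (Freedman, Schoenfeld, simulated) |
|---|---|---|---|
| none | 2.00 | 58.1 | 81.5%, 84.1%, 84% |
| 64 | (9/64)/(5/64) = 1.80 | 61.7 | 73%, 75%, 75% |
| 32 | (5/32)/(3/32) = 1.67 | 64.4 | 64%, 66%, 65% |
| 16 | (3/16)/(2/16) = 1.50 | 67.9 | 50%, 51%, 51% |

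This sizes transient improvement in general, not the death rule. For the death rule, each affected subject moves that arm's proportion improved by 1/36 = 2.8 percentage points.

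**Step 4. The Phase I gate.** If the subject in the first row is still in hospital on Day 15, SAP 13.1.1's condition makes that subject a responder and status on Day 15 does not. P(at least 2 of 14) = 1 − (1 − p)^14 − 14p(1 − p)^13 gives 15%, 42%, 80% and 95% at p = 5%, 10%, 20% and 30%. At the plan's own control assumption, p = 1 − 2^(−15/16) = 47.8% and the gate opens with probability 99.8%. The wording therefore matters mainly if improvement is uncommon.

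**The case against.** **Device changes.** A reader might infer that any one-day change of oxygen device is a success. The documents do not support that, as the table shows. Invasive and bilevel ventilation are excluded at entry, mask and cannula oxygen largely matches score 4, and the share entering at score 5 is not given. A change reversed before the day's last observation does not count either.

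**A two-day rule as the remedy.** A reader might also infer that false responses are common and that two-day confirmation nearly removes them. With an assumed independent daily chance of 2%, 1 − 0.98^27 = 42% of stable score-5 subjects would respond by Day 28, against 1.0% when two consecutive days are required. The 2% has no source in the documents, and the second figure depends on independence between days. If a dip has a 50% chance of lasting into the next day, confirmed false response is about 1 − (1 − 0.02 × 0.5)^26 = 23%. A two-day rule also misses the main example, because Days 8 and 9 are both ambulatory. Making confirmation the primary definition is a trade-off, not a correction.

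**Relapse is seen elsewhere.** Day 28 OSCI status, mortality, ventilation and oxygen-free days are separate endpoints, and Protocol 14.10 stops the study for a death by Day 15. This is true, but none of it changes how the primary analysis codes a death from Day 16 to Day 28 after an improvement.

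**Other endpoints.** Viral clearance needs two negative results, but NEWS2 improvement and pulmonary clearance need no confirmation, so the lack of confirmation for OSCI is not unusual within this plan.

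**The trial has closed.** SAP 15 records termination after 7 Phase I subjects. That limits the consequence; it does not correct the rule.

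**Conclusion.** The point holds as an inconsistency in the endpoint rules. As written, death after a first improvement is a success and death without one is a failure, and no planned analysis of the primary endpoint tests the difference. This follows from the text and needs no assumption.

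Its size in this population cannot be derived, because the documents give no rate of relapse, readmission or death after improvement. The fall in the rate ratio from 2.0 to between 1.8 and 1.5 rests on exponential times, medians of 8 and 16 days, and an assumed equal transient hazard.

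Phase II is open-label, and a reader might infer that a sustained definition would protect against that. It would not: a discharge or device decision influenced by knowledge of the arm usually still stands the next day.

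**What to change.** 1. **SAP 13.3, primary analysis.** Treat every subject who dies by Day 28 as not improved and censor at Day 28, whether or not an improvement was recorded earlier.
2. **SAP 13.4, new sensitivity analysis.** Require improvement to be held on consecutive daily OSCI scores with no return, through readmission or otherwise, to the baseline Patient State or worse through Day 28. Date the event to the first day of the held improvement. State what happens when the confirming score is missing; for example, count it as held if the next available score is still in the better state with no readmission or death between. A rule is needed because Protocol 6.1.4 specifies daily calls only through at least the Day 15 visit.
3. **Phase I gate.** Reconcile Protocol 14.6 and the Synopsis with SAP 13.1.1. Count a subject as a responder only if alive and still in the better Patient State at Day 15, using only data available at that decision. Deaths up to Day 28 cannot enter, because the DMC meets after the last subject's Day 15 (Protocol 14.11.2). State how a missing Day 15 score is handled.

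**Cost.** Mostly wording, since daily OSCI is already planned. The primary analysis has slightly fewer events, and the loss of power is small if death after improvement is rare. If 5% of subjects in each arm (about two per arm) lost their event, expected events would fall to 0.95 × 58.1 = 55.2 and one-sided power to 80% by Freedman, or from 84% to 76% by simulation with those subjects held event-free to Day 28. The sustained analysis could lose more: at 10% or 20%, simulated power is 68% or 54%. That is a reason to keep it as a sensitivity analysis.

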13.2 Efficacy Endpoints

The study includes the following efficacy endpoints:

- 1) Clinical status by OSCI at Day 28.
- 2) Clinical improvement by OSCI by Day 15.
- 3) Rate of clinical improvement by OSCI at Day 28. The rate is defined as the proportion of subjects who achieved clinical improvement by OSCI on or prior to Day 28.
- 4) Time to clinical improvement as measured by OSCI.
- 5) Time to clinical improvement by NEWS2. Time to clinical improvement by NEWS2 is defined as the time from the date of randomization (date of first dose of CYNK-001 for Phase 1) to the first date of clinical improvement by NEWS2. Clinical improvement by NEWS2 is defined as a 25% decrease compared to baseline in the NEWS2 Score. Subjects without clinical improvement by NEWS2 on or before Day 28 will be censored at Day 28.

- 6) Rate of clinical improvement by NEWS2 at Day 28. The rate is defined as the proportion of subjects who achieved clinical symptom improvement by NEWS2 Score on or prior to Day 28.
- 7) Rate of clearance of SARS-CoV-2 from mucosal specimens at Day 28. Rate is defined as the proportion of subjects with clearance of SARS-CoV-2 by rRT-PCR by two negative results at least 24 hours apart. Specimens included are nasopharyngeal swab and optional oropharyngeal swab.
- 8) Time to clearance of SARS-CoV-2 from mucosal specimens at Day 28. Clearance is defined as the time from the date of randomization to clearance of SARS-CoV-2 by rRT-PCR by two negative results at least 24 hours apart. Specimens included are nasopharyngeal swab and optional oropharyngeal swab.
- 9) Time to pulmonary clearance at Day 28. Clearance is defined as the time from randomization to the date of pulmonary clearance. This is defined as disappearance of virus from LRT specimen where it has previously been found (induced sputum and endotracheal aspirate if available).
- 10) Rate of pulmonary clearance at Day 28. Rate is defined as the proportion of subjects who had disappearance of virus from LRT specimens where it has previously been found.
- 11) Duration of hospitalization from date of hospitalization to date of medical discharge.
- 12) For subjects requiring supplemental oxygen, the days with supplemental oxygen-free up to Day 28.
- 13) Proportion of subjects who need invasive or non-invasive ventilation up to Day 28.
- 14) SOFA score for subjects admitted to the ICU from ICU admission to ICU discharge, up to Day 28.
- 15) Radiologic Evaluation Score at Day 28 using Chest x-ray and/or CT scans.
- 16) Proportion of subject who died up to Day 28 and up to Month 6.

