13.3 Analysis Methods

The primary endpoints will be analyzed with hypothesis testing procedures. No formal hypothesis will be carried out for secondary endpoints and the p-values are provided for informative purpose only.

Missing data and censoring will be handled as described below.

- **Primary Efficacy Analysis**

Phase II efficacy data will be analyzed for the ITT population based on randomized treatment group.

The primary efficacy endpoint is the time to clinical improvement on or before Day 28. Kaplan-Meier estimates of the survival curve, estimate of median survival time and its 95% CI will be calculated. Log-rank test will be used to test the difference between treatment groups while adjusting for pre-defined age strata.

Hazard ratio will be estimated via proportional hazard model using treatment as a factor stratified by age group.

Subjects who withdraw after randomization and before any measurements assessed will be censored at randomization date; subjects who terminate from the study before Day 28 without clinical improvement will be censored on the date of the last visit; and subjects who died without clinical improvement by OSCI will be censored on Day 28; subjects without clinical improvement ~~who have no event~~ on or before Day 28 will be censored on Day 28.

- **Secondary Endpoints Analyses**

The analysis will be based on the ITT population unless otherwise specified. Since the purpose of the analysis is for hypothesis generation, no multiplicity adjustment or adjustments for stratification covariates (age and site strata) will be made.

For the endpoints of event rate, including:

- Proportion of subjects who achieved clinical improvements by OSCI

- Proportion of subjects with clearance of SARS-CoV-2 by rRT-PCR
- Proportion of subjects who had pulmonary clearance by LRT specimens where it has previously been found
- Proportion of subjects who need invasive or non-invasive ventilation
- Proportion of subjects who died

The proportions and their two-side 95% CIs will be calculated. Fisher's exact test will be used to test the difference between treatment groups. If the subject has no data after baseline, the subject will be considered as failure in the analysis.

For endpoints of time to event, including:

- Time to clinical improvement measured by NEWS2 Score
- Time to clearance of SARS-CoV-2 by rRT-PCR testing
- Time to disappearance of virus from LRTI specimen
- Time from randomization to medical discharge

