- Duration of hospitalization (from time from hospitalization to medical discharge up to Day 28)

The Kaplan-Meier method will be used for estimating the survival curves, the median survival time and its two-sided 95% confidence interval will be estimated. [REDACTED]

[REDACTED]

Mortality rate will be provided and be compared using Fisher's Exact Test.

For the endpoint of proportion of subjects who achieved clinical symptom improvement by NEWS2 Score by Day 28, clinical improvement is defined as a 25% reduction in NEWS2 Score. The proportions

and their two-sided 95% CIs will be calculated. Fisher's exact test will be used to test the difference between groups. If the subject has no data after baseline, the subject will be considered as failure in the analysis.

1) Calculation

- a. Respiratory rate, oxygen saturation, temperature, systolic blood pressure, and heart rate will be collected on the Vital Signs and Oxygen Saturation eCRF forms.
- b. Consciousness score will be based on the Physical Exam eCRF form. If Neurological is normal, then NEWS2 Consciousness will be scored as zero. If Neurological is abnormal, then the score will be determined based on the comments. A clinical review of the comments from the abnormal neurological findings will be required.
- c. Air or Oxygen will be based on the eCRF form Prior and Concomitant Procedure and Surgeries. If a subject had Preferred Term "Oxygen Therapy" then the NEWS2 Air or Oxygen Score will be 2 for the days from the start day through the end day of the procedure.
- d. Calculation of overall NEWS2 Score for a given day will be the sum of the scores from respiratory rate, oxygen saturation, temperature, systolic blood pressure, heart rate, consciousness, and air or oxygen categories. For infusion days, data for Vital Signs and Oxygen Saturation are collected 3 separate times. For infusion days, a separate overall score will be calculated for each time the Vital Signs and Oxygen Saturation is collected, and the worst overall score will be used as the NEWS2 Score for that day.

2) Missing data handling:

- a. If a measure for vital signs and oxygen saturation is missing, corresponding NEWS2 score will be set as missing, and the overall NEWS2 score takes the form $\geq xx$. If all categories from vital signs and oxygen saturation is missing, the overall NEWS2 score will be set as missing.

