14.7 Infectious Symptom Assessment

The infectious symptom assessment will be tabulated over time with the proportion of clinical status assessment as defined in the CRF. The descriptive statistics, including the proportion and its 95% confidence interval will be provided.

No missing data will be imputed for this part of analysis nor formal hypothesis testing will be performed.

Subject level listing of AEs, vital signs, laboratory assessments and inflammation assessments will be provided.

15. Changes in Conduct or Planned Analyses from the Protocol

Description of change of conduct: Early termination of the study by the company.

In review of the current status and enrolment challenges of the CYNK-001-COVID-19 clinical trial and given the current landscape of the COVID-19 pandemic and the rollout COVID-19 vaccine, a decision by

Celularity has been made to close the CYNK-001-COVID-19 clinical trial. As a result of this early termination, only 7 patients were enrolled and dosed in the Phase I portion.

Due to this change, a brief clinical study report will be provided instead of a full CSR. Based on this change, only the following analysis will be provided for Phase I along with supporting listings:

- Summary of Subject disposition
- Summary of major protocol deviations
- Summary of demographics and baseline characteristics
- Analysis of time to clinical improvement by NEWS2 score
- Analysis of rRT-PCR tests and time to clearance of SARS-CoV-2 by rRT-PCR results (if enough data available)
- Analysis of SOFA scores (if enough data available)
- Summaries of adverse events
- List of deaths
- Summaries of laboratory results, shift from baseline and abnormal laboratory values
- Summaries of vitals signs, oxygen saturation and ECG and shifts from baseline
- Summary of abnormal post-baseline QTc results

16. Analysis of Concomitant Medication and Concomitant Procedure

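### NEWS2 improvement is a 25% fall from baseline, but entry sets no minimum NEWS2, so an eligible subject who starts at 0 cannot meet the definition as worded

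*SAP*

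**What the plan says.** **Definition.** SAP 13.2 item 5 states: "Clinical improvement by NEWS2 is defined as a 25% decrease compared to baseline in the NEWS2 Score". SAP 13.3 repeats it for the rate: "clinical improvement is defined as a 25% reduction in NEWS2 Score". Protocol 6.9 gives no threshold; it refers only to symptoms improving as measured by NEWS2.

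**Subjects who do not improve.** For the time endpoint, SAP 13.2 item 5 says: "Subjects without clinical improvement by NEWS2 on or before Day 28 will be censored at Day 28". For the rate, item 6 says: "The rate is defined as the proportion of subjects who achieved clinical symptom improvement by NEWS2 Score on or prior to Day 28".

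**Who is analysed.** For Phase II secondary endpoints, SAP 13.3 says: "The analysis will be based on the ITT population unless otherwise specified". Phase I analyses use the safety set (SAP 4.8). Neither carries a condition on baseline NEWS2.

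**Who can enter.** Protocol 8.1, criterion 2, requires: "Subject is experiencing any symptom/clinical sign of COVID-19 illness or has a positive disease-related chest x-ray/CT scan at screening". Criterion 6 sets a lower limit on SpO2 and allows oxygen without requiring it. No criterion in Protocol 8.1 or 8.2 mentions NEWS2.

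**What survives closure.** SAP 15 records that the trial closed with 7 subjects dosed in Phase I. Its short list of analyses still to be done includes "Analysis of time to clinical improvement by NEWS2 score". The NEWS2 rate is not on that list.

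**The concern.** A percentage fall needs something to fall from. NEWS2 adds up points for vital signs, oxygen use and consciousness, so a subject on room air with normal observations scores 0. Entry allows such a subject: one symptom is enough, and Protocol 12.1.3 names sore throat, headache and loss of taste or smell, none of which earns NEWS2 points. A positive film without symptoms also suffices.

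The mildest eligible subjects could then be reported as never improving, which pulls down the estimated improvement curve and the rate. The alternative coding errs the other way and credits a subject who has not changed. Two programmers working from the same SAP could report opposite outcomes for the same person.

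**Working it through.** The plan states no figure for the NEWS2 endpoints, so there is none to reproduce. Its only power figure (at least 81%) is for time to OSCI improvement and plays no part here.

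**Step 1. Can an eligible subject score 0?** Appendix C keys each item from 0 to 3. On the visible chart, no points are shown for a respiratory rate of 12 to 20, SpO2 of 96% or more on Scale 1, or breathing air. SAP 13.3 scores consciousness 0 when the neurological examination is normal, adds 2 only while oxygen therapy is recorded, and sums the items. The lowest total is therefore 0. A subject with loss of taste, SpO2 of 96% or more on air and otherwise normal observations meets criteria 2 and 6 and scores 0.

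**Step 2. Which follow-up scores qualify?** Read the rule as at least 25%: (baseline − score) / baseline ≥ 0.25, with whole-number scores.

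| Baseline | Highest qualifying score | Fall needed |
|---|---|---|
| 0 | none (0/0 if unchanged) | not possible |
| 1 to 4 | baseline − 1 | 1 point |
| 5 to 8 | baseline − 2 | 2 points |
| 9 to 10 | baseline − 3 | 3 points |

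Within this range, 0 is the only baseline from which no improvement can be reached.

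**Step 3. Same rule, other coding.** Written as score ≤ 0.75 × baseline, a baseline of 0 gives 0 ≤ 0, which is true. The subject counts as improved at the first later score of 0. At no other baseline does an unchanged score qualify.

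**Step 4. Effect on the retained Phase I analysis.** Let k of the 7 subjects start at 0 and be followed to Day 28. Under the rule as worded they remain at risk throughout, so Kaplan-Meier cumulative improvement by Day 28 cannot exceed (7 − k)/7:

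- k = 1: 6/7 = 86%
- k = 2: 5/7 = 71%

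These ceilings apply even if every other subject improves. Earlier censoring among the others can only lower them.

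**Step 5. General ceiling.** With a share f at baseline 0, the highest attainable improvement proportion is 1 − f. The documents do not give f. For an assumed 10%, 20% or 30%, the ceiling is 90%, 80% or 70%.

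**Step 6. How the SAP treats comparable endpoints.** In SAP 13.2, pulmonary clearance (items 9 and 10) counts only specimens in which virus was found before. Oxygen-free days (item 12) are limited to subjects who need oxygen, and SOFA (item 14) to those admitted to the ICU. Items 5 and 6 have no equivalent condition.

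**The case against.** **The case may not arise.** All Phase I subjects are inpatients. Protocol 12.1.4 records the worst vital signs on non-infusion days, and SAP 13.3 takes the worst of three scores on infusion days. Any oxygen therapy adds 2 points, and SpO2 of 95% or less on Scale 1 adds at least 1. A score of 0 needs every component normal at its worst, and perhaps none of the 7 subjects met that. This stands as a limit on size. It does not supply the missing rule.

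**The SAP does not call these subjects failures.** A reader might infer that it does. Its explicit sentence is narrower: "If the subject has no data after baseline, the subject will be considered as failure in the analysis". A subject at baseline 0 with follow-up data falls outside it. Non-improvement in the rate follows from the definition and the denominator; in the time analysis the consequence is censoring at Day 28. Because coding could reverse the result, a bias in one direction is not established.

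**A loss of Phase II power.** A reader might also borrow the plan's 8-day and 16-day figures and compute how power falls as the share at 0 rises. The documents do not support that use. Those times and the one-sided 0.05 belong to the OSCI sample size. SAP 4.5 judges p-values at two-sided 0.05, and SAP 13.3 makes secondary p-values informative only. The trial closed in Phase I. Part of any such loss would also remain after the exclusion, because fewer subjects would be analysed.

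**Redaction and ITT.** Text is blacked out in SAP 13.3 after the Kaplan-Meier sentence for secondary endpoints, so a restriction there cannot be ruled out. The visible definitions in items 5 and 6 carry none. Excluding subjects does depart from full ITT; that cost is real but small.

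**Conclusion.** The point holds in limited form. The definition cannot be met from a baseline of 0, entry permits that baseline, and the visible text has no rule for it. This is a fault in the stated rule, because the censoring provision then classifies such a subject as not improved.

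The size is unknown. The ceilings of 86% and 71% among 7 subjects are conditional on one or two of them starting at 0; the ceilings of 90%, 80% and 70% rest on an assumed share. All of them read the rule as at least 25%, and the Phase I figures assume follow-up to Day 28. If nobody starts at 0, no result changes.

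The reach is one secondary endpoint. Time to OSCI improvement and its stated power are untouched. After closure, what remains live is Day 28 censoring in the Phase I time analysis.

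**What to change.** In SAP 13.2 items 5 and 6, in SAP 13.3, and for the analysis kept in SAP 15:

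- Limit time to NEWS2 improvement, and the rate if it is reported, to subjects with baseline NEWS2 of at least 1.
- Report the number left out (by arm in Phase II).
- List the NEWS2 course of every subject who starts at 0, including any who worsen.

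Stating the rule as a percentage decrease with a baseline above 0 also removes the coding ambiguity. The entry criteria need not change.

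The cost is about one sentence in the SAP and a listing. Fewer subjects enter this secondary analysis, and it departs from full ITT. The subset is fixed at baseline, so in a randomised phase the comparison between arms would be preserved, and nobody left out could have met the definition. A subject who starts at 0 and deteriorates drops out of the NEWS2 estimate, which is why the listing is needed. Keeping everyone in under an explicit, pre-specified rule for baseline 0, with a count, would also close the gap, but it would leave subjects who cannot improve in the estimate or credit unchanged subjects with improvement.
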